5.1.1 Screening Phase

The screening phase will last for up to 28 days. The screening phase begins by establishing the participant's initial eligibility and signing of the informed consent form (ICF). Participants will be enrolled using the Interactive Response Technology (IRT).

If a participant surpasses the 28-day window during the screening phase because of a study-related procedure (eg, scheduling of a tumor biopsy or waiting time for a study-related laboratory value),

the participant must be re-consented but does not need to be assigned a new participant identification number. In this situation, the least amount of repeat procedures from the initial screening to qualify the participant while maintaining safety and eligibility under the discretion of the BMS Medical Monitor and investigator may be done to reduce any undue burden of procedure in this population.

5.1.2 Treatment Phase

The treatment phase consists of up to twenty-six 4-week treatment cycles. Each treatment cycle is comprised of a daily oral dose of BMS-986242 and 1 dose of nivolumab administered IV Q4W on Day 1 of the treatment cycle. In addition, dose escalation will start with Cycle 0, a lead-in period of 2-week duration, during which monotherapy with BMS-986242 is administered. The total treatment period is 104 weeks or 26 cycles. This is in addition to the 2-week Cycle 0.

Following every 2 treatment cycles (8 weeks), the decision to treat a participant with additional cycles of study treatment will be based on radiological tumor assessments (initial evaluation performed at baseline, end of Cycle 2, and every 8 weeks). Assessments of partial response (PR) and complete response (CR) must be confirmed at least 4 weeks following initial assessment. Tumor progression or response endpoints will be assessed using Response Evaluation Criteria in Solid Tumors (RECIST) v1.1 criteria for solid tumors ([Appendix 6](#)).

Treatment beyond progression may be allowed in select participants with initial RECIST v1.1-defined progressive disease (PD) after discussion and agreement with the BMS Medical Monitor that the benefit/risk assessment favors continued administration of study treatment (eg, participants are continuing to experience clinical benefit as assessed by the investigator, tolerating treatment, and meeting other criteria specified in [Section 5.1.2.3](#)).

Participants with a response of stable disease (SD), PR, or CR at the end of a given cycle will continue to the next treatment cycle. Participants will generally be allowed to continue study treatment until the first occurrence of either: 1) completion of the maximum number of cycles, 2) PD, 3) clinical deterioration suggesting that no further benefit from treatment is likely, 4) intolerability to study treatment, or 5) the participant meets criteria for discontinuation of study treatment as outlined in protocol [Section 8](#). Individual participants with confirmed CR will be given the option to discontinue study treatment on a case-by-case basis after specific consultation and agreement between the investigator and BMS Medical Monitor in settings where benefit/risk justifies discontinuation of study treatment.

5.1.2.1 Part 1: Dose Escalation

Six disease-restricted populations will be included in the dose-escalation part. These are melanoma, NSCLC, SCCHN, RCC, BUC, and gastric cancer. The dose-escalation part of the study will evaluate doses of BMS-986242 in combination with nivolumab based on DLTs using a BLRM model (for BMS-986242 monotherapy lead-in) and BLRM-copula model (for BMS-986242 in combination with nivolumab). The Bayesian models will be used for recommendation of the next dose to be investigated. BLRM (combined with copula) framework with an escalation with overdose control principle will be employed to ensure that safety is not compromised during dose escalation.

The initial dose level of BMS-986242 will be 12.5 mg administered orally daily. After a 2-week period, once initial lead-in monotherapy (Cycle 0) is deemed tolerable, combination with 480 mg flat dose nivolumab (Cycle 1) will be initiated.

Dose levels to be considered for the next combination cohort (with monotherapy lead-in) will be based on recommended monotherapy dose from BLRM and recommended combination dose from BLRM-copula. The lower dose from these 2 recommendations will be considered. Potential dose levels for dose escalation are provided in [Table 5.1.2.1-1](#). The maximum allowable increase in dose will be 100%. Final dose selection for the next cohort/dose level will be made in conjunction with all data available from PK and pharmacodynamic assessments, and will be made after discussion and agreement between investigators and BMS Medical Monitor. Accordingly, intermediate or lower doses, or less frequent dosing of BMS-986242 may be tested if none of the planned doses/schedules are found to be tolerated as the lead-in phase or in combination with nivolumab.

Initially, approximately 4 participants will be treated at the starting dose level of BMS-986242. During the dose-escalation phase, once a dose level has been decided, a set of approximately 4 participants will be initially treated at that specified dose level. Increments of approximately 3 participants will be added to each dose level depending on model recommendation and clinical judgment. Due to the potential for early discontinuation, additional participant(s) may be enrolled to ensure at least 3 evaluable participants at each dose level.

Cohort tolerability assessment and subsequent dose recommendation may occur when 2 DLT-evaluable participants within a cohort have completed the 6-week DLT observation period (see [Section 7.4.1](#) for criteria for DLTs). DLTs occurring within the 2-week lead-in period (DLT observation period for monotherapy) will be used to fit the BLRM model for monotherapy. DLTs occurring within the 4 weeks of combination period (DLT observation period for combination) will be used to fit the BLRM-copula model. If a potential DLT occurring in any third evaluable participant does not influence the dose recommendation by BLRM (-copula), then the BLRM (-copula)-recommended next dose level may proceed without waiting for the third participant to complete the corresponding DLT observation period after discussion and agreement by the sponsor and investigators. The lower recommended dose from both models will be considered for the next dose escalation. Participants receiving $\geq 75\%$ (11 out of 14 doses) of BMS-986242 in the 2-week lead-in cycle will be considered as DLT-evaluable participants for BMS-986242 monotherapy. Participants who receive at least 1 dose of nivolumab and have been followed at least 5 days and receive $\geq 75\%$ BMS-986242 (21 out of 28 doses) in the 4-week DLT observation period for combination therapy will be considered as DLT-evaluable participants. Continuous re-assessment of dose recommendation by BLRM will be carried out at each dose level after each cohort of participants with consideration of all available DLT information. In order to allow additional safety, PK, and pharmacodynamic assessment, in Part 1 up to 12 additional participants may be enrolled at any dose level at or below the MTD, up to a total of 24 additional participants.

No intra-participant dose escalation is allowed, although dose modifications of BMS-986242 may be permitted (see [Table 7.4.2-1](#)).

[figure not shown]
Sentinel Participant: During dose escalation, a staggered dosing (sentinel participant) approach will be used. In the first dose level, the first participant in both lead-in and combination will receive the Cycle 0 Day 1 or Cycle 1 Day 1 dose(s) of study treatment(s) and be observed for 5 days before additional participants in that cohort receive monotherapy or combination study treatment. In subsequent dose levels, a sentinel participant with a 5 day observation period will be used for Cycle 0 Day 1.

The dose-escalation planned dose levels for selection of the MTD/MAD/alternative dose is depicted in Table 5.1.2.1-1 and [Figure 5.1.2.1-1](#).

Table 5.1.2.1-1: Dose Escalation Schedule

Dose Level	BMS-986242	Nivolumab
1	12.5 mg	480 mg IV Q4W
2	25 mg	480 mg IV Q4W
3	50 mg	480 mg IV Q4W
4	100 mg	480 mg IV Q4W
5	200 mg	480 mg IV Q4W
6	400 mg	480 mg IV Q4W
7	600 mg	480 mg IV Q4W

Figure 5.1.2.1-1: Study Design Schematic - Dose Escalation

Clinical Pharmacology Substudy:

A clinical pharmacology substudy will be conducted to characterize the PK profile of BMS-986242 after a single-dose administration, BMS-986242 exposure-QTc relationship and to evaluate of the effect of food on the bioavailability of BMS-986242. The substudy will evaluate selected dose levels that have already been determined to be tolerable during dose escalation.

Participants in the substudy will receive a single dose of BMS-986242 under fasting condition on Cycle 00 (Day 1) followed by a 7-day washout period during which serial PK samples will be collected (Table 9.5.3-2). Triplicate ECGs will be collected at predose and select time points postdose on Day 1 (with matching PK samples) to allow the assessment of the effect of BMS-986242 exposure on QTc intervals. All participants will then receive BMS-986242 under the usual dosing condition with a light meal once daily in combination with nivolumab on Cycle 1 Day 1 and will follow all assessments as per Table 2-3. The inclusion criteria used in the dose-escalation phase apply to participants enrolled in the clinical pharmacology substudy (Section 6.1). The doses to be evaluated in the substudy will be determined based on available safety, PK and biomarker data. At least 3 doses (below, at, and above the expected dose for expansion) are expected to be evaluated in at least 6 evaluable participants per dose level in the substudy. Additional dose levels at may be evaluated if warranted.

At a designated dose level, an exploratory food effect evaluation will be conducted. After receiving a single dose of BMS-986242 under fasting condition on Cycle 00 (Day 1) followed by a 7-day washout period, participants will receive 1 dose of BMS-986242 with a high-fat meal on Day 8. Serial PK samples will be collected during a 2-Day washout period (Table 9.5.3-2). Participants will then receive BMS-986242 under the usual dosing condition with a light meal once daily in combination with nivolumab on Cycle 1 Day 1 and will follow all assessments as per Table 2-3. For the dose to be evaluated in the food effect substudy, either a higher dose would need to be demonstrated to be safe in the dose-escalation phase or sufficient exposure multiples should have been obtained following multiple doses at the same dose level. Additional doses may be evaluated if warranted.

Study design schematics for the clinical pharmacology substudy are shown in Figure 5.1.2.1-2 (single-dose PK and exposure-QTc assessment) and Figure 5.1.2.1-3(food effect).

Figure 5.1.2.1-2: Study Design Schematic for the Clinical Pharmacology Substudy
Single-dose PK and Exposure-QTc Assessment (Selected Dose Levels)

[figure not shown]
[figure not shown]

Figure 5.1.2.1-3: Food Effect Assessment (Designated Dose Group*)
Food Effect Assessment (Designated Dose Group*)

* A designated dose group from the selected dose levels will be evaluated for both single-dose

PK/exposure-QTc and food effect. One cohort of at least 6 evaluable participants will be included.

Up to approximately 78 participants are planned to be enrolled for Part 1 (dose escalation) and clinical pharmacology substudy: approximately 30 participants for the dose-escalation phase, with up to 24 additional participants in Part 1 for additional characterization of the safety, PK, and pharmacodynamic profile of BMS-986242, and approximately 24 participants for the clinical pharmacology substudy (including food effect).

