3 DECISION RULE FOR DOSE ESCALATION AND SIMULATION

Dose escalation recommendations for BMS-986242 monotherapy and in combination with nivolumab will be based on the inference from the Bayesian posterior and the probability that the true DLT rate for each dose lies in 1 of the following categories:

- [0%, 16%) under-dosing
- [16%, 33%) targeted toxicity
- [33%, 100%] excessive toxicity

These boundaries are similar to the toxicity boundaries used by a rule-based design (ie, 3 + 3 design) in that a minimum is set at 16% (about 1 in 6) DLT rate and a maximum at 33% (about 2 in 6) DLT rate. Following the principle of EWOC, dose recommendations for the next cohort will be based on the Bayesian model after DLT information becomes available during the DLT period, accounting for all of the available data from the administered doses, and the candidate doses are the ones fulfilling the overdose criterion that there is less than 25% (for monotherapy) and 35% (for combination therapy) chances of excessive toxicity. Only the candidate doses will be considered for the next cohort. While the Bayesian model will use DLT information from the DLT period only, clinical assessment will take into consideration of the totality of available data including PK/Pharmacodynamics from all treated participants.

The MTD is the highest administered dose not expected to cause DLT in more than 33% of the treated participants during the DLT period. The final recommended MTD/RP2D will be based on the recommendation from the BLRM/BLRM-copula, and on an overall assessment of all available safety, PK/Pharmacodynamic, and efficacy data.

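### The early-escalation look-ahead tests one pending participant although cohorts start with about four; a second pending DLT goes untested, and at the 400 to 600 mg combination step it would reverse the recommendation

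*Combined protocol and SAP*

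**What the plan says.** Section 5.1.2.1 sets the cohort size: once a level is chosen, "a set of approximately 4 participants will be initially treated at that specified dose level". Allowing for early discontinuation, "additional participant(s) may be enrolled to ensure at least 3 evaluable participants at each dose level".

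The same section sets the decision time: "Cohort tolerability assessment and subsequent dose recommendation may occur when 2 DLT-evaluable participants within a cohort have completed the 6-week DLT observation period". It then gives the look-ahead condition, "If a potential DLT occurring in any third evaluable participant does not influence the dose recommendation by BLRM (-copula"), under which the recommended next dose "may proceed without waiting for the third participant to complete the corresponding DLT observation period after discussion and agreement by the sponsor and investigators". A fourth participant is not mentioned. Lead-in DLTs (2 weeks) feed the BLRM and combination DLTs (4 weeks) feed the BLRM-copula. On combining the two models: "The lower recommended dose from both models will be considered for the next dose escalation".

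Appendix 7, Section 3 defines candidate doses as those for which "there is less than 25% (for monotherapy) and 35% (for combination therapy) chances of excessive toxicity", where excessive means a true DLT rate of 33% or more. Among the candidates, Section 4 of that appendix picks the dose most likely to have a DLT rate between 16% and 33%. The simulations in Section 3.1 use a fixed cohort of 3.

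**The concern.** The look-ahead exists so that a decision taken on incomplete data agrees with the one the complete data would give. With three evaluable participants it does this in full: two outcomes are known and the third is set to its worst value. With four, two can be pending and only one is set to its worst value. The next dose could therefore be open, with participants on it, when the second pending DLT is reported and the completed cohort no longer supports that dose under the overdose limit. Because the simulations use cohorts of 3, the reported operating characteristics do not cover this four-person situation.

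**Working it through.** **Inputs.** From Appendix 7:
- Monotherapy prior (Table 1): log α1 ~ N(−0.847, SD 1.53), log β1 ~ N(0, SD 1), correlation 0, reference dose 600 mg.
- Nivolumab prior (Table 3): means (−3.269, −0.152), SDs (1.186, 0.771), correlation −0.369.
- Interaction γ: gamma distribution with mean 1.1 (Section 2.2.3).
- Limits: P(DLT rate ≥ 33%) below 25% (monotherapy) and below 35% (combination).

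**Assumptions.** The ratio of 480 mg nivolumab to its mg/kg reference dose is not given, so I used 0.5, 1 and 2. The spread of γ cannot be taken as written: the stated 97.5th percentile, log(3) = 1.0986, lies below the stated mean of 1.1. I used shape 13.5, which gives the stated 40% probability below 1, and shape 50.

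**Formulas.** Monotherapy: logit p = log α1 + β1 log(dose/600). Combination: P = 1 − exp(−[{−log(1−p)}^(1/γ) + {−log(1−q)}^(1/γ)]^γ), with q the nivolumab DLT probability. The monotherapy posterior was computed on a grid and the combination posterior by importance sampling.

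**Reproducing the plan's example first.** After 0/3 and 0/3 at 25 mg, Section 4 recommends 400 mg with a target-interval probability of 27% and excludes 600 mg. The rebuilt model recommends 400 mg and excludes 600 mg in every variant (overdose at 600 mg 0.41 to 0.49). Its target probability at 400 mg is 0.28 at ratio 0.5, 0.30 to 0.31 at ratio 1 and 0.33 to 0.35 at ratio 2. The decision reproduces throughout; the 27% is matched closely only at ratio 0.5.

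**Combination, 400 to 600 mg.** History: 0/4 in both periods at all lower doses and 0/4 in the lead-in at 400 mg. Two participants have completed combination without a DLT and two are pending.

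| Combination data at 400 mg | P(overdose at 600 mg) | Model recommends |
|---|---|---|
| 1/3 (the check as written) | 26 to 27% | 600 mg, check passes |
| 2/4 (both pending are DLTs) | 41 to 44% (limit 35%) | 400 mg |

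This holds in all six ratio and shape variants, with or without the 100% cap on dose increases. The monotherapy model does not stop the step: with 0/4 in the lead-in, its overdose probability at 600 mg is about 14 to 15%, under 25%.

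**Combination, other steps, at 2/4 with the lead-in complete** (shape 13.5, three ratios):
- From 25 mg: 8 to 13%. From 50 mg: 6 to 8%. From 100 mg: 11 to 12%. From 200 mg: 27 to 30%. All are under 35%.
- From 12.5 to 25 mg: about 23.5% at ratio 0.5, 24 to 25% at ratio 1 and 35 to 36% at ratio 2. Only ratio 2 crosses the limit.

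**Monotherapy, limit 25%, 0/4 at lower doses.**

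| Step | 1/3 | 2/4 |
|---|---|---|
| 25 to 50 mg | 12.5% | 32.8% |
| 50 to 100 mg | 10.5% | 27.8% |
| 100 to 200 mg | 15.6% | 35.7% |

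These three follow the same pattern, on two conditions. First, the two pending participants must still be in the 2-week lead-in when two others finish 6 weeks, so they must have started more than 6 − 2 = 4 weeks after the second completer. Second, the recommendation must mean the next dose under the 100% cap. Read without the cap, one hypothetical DLT already changes it (25 mg: 400 to 100; 50 mg: 400 to 100; 100 mg: 400 to 200), so the existing check forces a wait. At 12.5, 200 and 400 mg the existing check blocks anyway, because 1/3 gives 28%, 31% and about 42 to 43%.

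**How often.** For a common true rate p and independent outcomes, P(0/2 then 2/2) = (1−p)²p². At 33%: 0.67² × 0.33² = 0.4489 × 0.1089 = 4.9%. At 40%: 0.36 × 0.16 = 5.8%. At 50%: 0.25 × 0.25 = 6.3%. At the 2 to 7% that Table 4's first two scenarios assume for monotherapy at 25 to 100 mg, it is 0.04 to 0.4%.

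**The case against.** The strongest reply is that the plan has other brakes. Opening early needs sponsor and investigator agreement, the lower of two model recommendations applies, increases are capped at 100%, a sentinel participant is observed for 5 days at the next dose, and the model is re-assessed as DLT data arrive. In addition, about 4 may simply allow for dropout; with exactly three evaluable, the check is complete. All of this stands, and it rules out calling the look-ahead the only protection. But none of these provisions counts a fourth pending outcome. Agreement is a matter of judgment, re-assessment sees the second DLT only after the next dose is open, and the lower-of-two rule does not bind at 400 to 600 mg.

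A reader might infer that the next dose opens in breach of the overdose rule. The documents do not support that: Appendix 7, Section 3 applies the limit to the data available, and 0/2 at opening satisfies it. The conflict appears only if both pending participants later have DLTs.

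A reader might also infer a gap at every dose, or quote the chance that two pending participants both have DLTs (11% at a true 33%, 25% at 50%) as its frequency. The first fails on the step-by-step results. The second leaves out the two completers without a DLT; the full paths are 4.9% and 6.3%.

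**Conclusion.** The point holds as a gap in the wording of the look-ahead, with one robust demonstration. At the 400 to 600 mg combination step the check passes at 26 to 27%, while the completed cohort could stand at 41 to 44% against a limit of 35%. That result assumes no DLTs at lower doses, a clean lead-in at 400 mg, four evaluable participants, a nivolumab ratio of 0.5 to 2 and γ shape 13.5 or 50; histories with DLTs at lower doses were not computed. The monotherapy cases at 25, 50 and 100 mg are conditional on late enrolment and the capped reading, and the 12.5 to 25 mg combination step on ratio 2. The path is uncommon, about 5% at a true rate of 33%, but it is the kind of situation that overdose control is meant to handle. The other safeguards reduce the gap without closing it.

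**What to change.** In Section 5.1.2.1, reword the condition along these lines: *the next dose level may open without waiting only if the recommendation is unchanged when every treated participant at the current dose level who has not completed the corresponding DLT observation period is counted as having a DLT, in the BLRM and in the BLRM-copula.* The same sentence should state whether the recommendation is taken before or after the 100% cap, since the monotherapy results turn on it. With one pending participant the rule works as it does now. No dose, limit, prior or DLT definition changes. The cost is one sentence, one or two extra model runs per decision, and an occasional wait of a few weeks.

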7.2 Method of Treatment Assignment

During the screening visit, the investigative site will call into the enrollment option of the IRT designated by BMS for assignment of a 5-digit participant number that will be unique across all sites. Enrolled participants, including those not dosed, will be assigned sequential participant numbers starting with 00001 (eg, 00001, 00002, 00003... 00010). The participant identification number will ultimately be composed of the site number and participant number. For example, the first participant screened (ie, enrolled) at site number 1 will have a participant identification number of 0001 00001. Once it is determined that the participant meets the eligibility criteria following the screening visit, the investigator site will call the IRT within 3 days prior to the first study treatment administration for the participant to be assigned to a treatment group.

During dose escalation, participants who are not evaluable for DLT determination may be replaced. Replacement participants will be assigned to the same treatment but will be assigned a new participant number.

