7.4 Dosage Modification

7.4.1 Dose-limiting Toxicity

For the purpose of guiding dose escalation, DLTs will be defined based on the incidence and grade of AEs for which no alternate cause can be identified.

Part 1: Cycle 0 BMS-986242 (monotherapy lead-in) will have a 2-week DLT evaluation period (DLT1). The combination regimen will have 4-week DLT evaluation period (DLT2). Therefore, the total DLT assessment period is 6 weeks. Participants may proceed from Cycle 0 to Cycle 1 at each cohort unless any of the following events is observed: any DLT, Grade 2 or higher immune-related AEs considered related to BMS-986242 (eg, immune-mediated pneumonitis, colitis, hepatitis, nephritis, renal dysfunction) with the exception of immune-mediated hypothyroidism and hyperthyroidism, or Grade 2 AST and ALT elevation that does not resolve to Grade 1 within 1 week. For Grade 2 AST and ALT elevations that resolve to Grade 1 or baseline within 1 week, participants can be rechallenged with BMS-986242 monotherapy for a minimum of 5 days before proceeding to combination with nivolumab provided there is not a recurrence of Grade 2 event.

The total DLT period is 6 weeks, and participants must have received at least 75% of the BMS-986242 doses and 1 dose of nivolumab with observation for a minimum of 21 days following the first combination treatment dose to be considered evaluable for dose escalation decisions. Based on the predicted human half-life of BMS-986242 of 13 hours, this interval is expected to cover the anticipated timeframe for the occurrence of clinically significant immediate and early-onset AEs related to BMS-986242 monotherapy during Cycle 0 and repeat dosing of BMS-986242 in combination with nivolumab in Cycle 1.

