D. Hematologic DLT

- Grade 4 neutropenia \geq 5 days in duration
- Grade 4 thrombocytopenia or Grade 3 thrombocytopenia with bleeding or any requirement for platelet transfusion
- Grade \geq 3 febrile neutropenia for 48 hours
- Grade \geq 3 hemolysis (ie, requiring transfusion or medical intervention such as steroids)
- Grade 4 anemia not explained by underlying disease
-

• In addition to the above criteria, any toxicity that results in a participant not receiving at least 75% of the doses of BMS-986242 and the dose of nivolumab during the DLT evaluation period or causing greater than 2 weeks of dose delay will be classified as a DLT.

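### DLT-evaluability is defined by doses and observation with no alternative for participants who had a DLT, so Section 7.4.1 read literally excludes every lead-in DLT and contradicts the passages that count them

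*Combined protocol and SAP*

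**What the plan says.** Section 5.1.2.1 gives one evaluability rule per DLT period. For the lead-in it is at least 75% of doses: "11 out of 14 doses) of BMS-986242 in the 2-week lead-in cycle will be considered as DLT-evaluable participants for BMS-986242 monotherapy". For the combination it is at least one nivolumab dose, at least 5 days of follow-up and 21 of 28 BMS-986242 doses.

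Section 7.4.1 gives a third rule, over the 6-week period. Participants "must have received at least 75% of the BMS-986242 doses and 1 dose of nivolumab with observation for a minimum of 21 days" after the first combination dose "to be considered evaluable for dose escalation decisions". The same section controls entry to combination treatment: "Participants may proceed from Cycle 0 to Cycle 1 at each cohort unless any of the following events is observed: any DLT".

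Section 7.4.1.1 classes as a DLT "any toxicity that results in a participant not receiving at least 75% of the doses of BMS-986242" and the nivolumab dose in the DLT period. Section 7.2 says that "participants who are not evaluable for DLT determination may be replaced", with no exception for a DLT. Section 7.4.1 limits replacement after withdrawal to reasons other than a DLT.

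Other passages count DLTs without an exposure condition. In Section 5.1.2.1, "DLTs occurring within the 2-week lead-in period (DLT observation period for monotherapy) will be used to fit the BLRM model for monotherapy". Section 7.4.1 has DLTs within 6 weeks guide escalation. Section 7.4.2 attributes a DLT after a dose reduction to the highest dose given. Appendix 7 Section 3 uses all available data, and Appendix 7 Sections 4 and 4.1 work through lead-in DLTs in participants who then receive no combination treatment.

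**The concern.** An exposure minimum normally screens out participants without a DLT who were observed too little to be called DLT-free. Here it is written for everyone. Section 7.4.3 requires treatment to be held after a DLT, so the participants most likely to miss a dose minimum are those with early toxicity.

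In a first-in-human escalation the evaluable set supplies the numerator and denominator of the model. It also controls timing, because Section 5.1.2.1 lets a recommendation start from two DLT-evaluable participants. If someone with a DLT is treated as non-evaluable and replaced, a result of staying at the dose, or of no admissible dose, can become an escalation.

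**Working it through.** **1. Thresholds.** 0.75 × 14 = 10.5, so 11 doses (11/14 = 78.6%; 10/14 = 71.4% fails). 0.75 × 28 = 21. Both agree with Section 5.1.2.1.

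**2. The rules applied to participants with a DLT.**

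| Participant | 5.1.2.1 lead-in | 5.1.2.1 combination | 7.4.1 |
|---|---|---|---|
| Lead-in DLT, 11 or more doses | meets | never starts | fails: no combination dose |
| Lead-in DLT, 10 or fewer doses | fails | never starts | fails: no combination dose |
| 14/14 lead-in, then 20/28 because of toxicity, with nivolumab and 21 days | meets | fails (71.4%) | fails per period; meets if pooled (34/42 = 81%) |

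So every lead-in DLT fails Section 7.4.1, while the loss under Section 5.1.2.1 is partial. A DLT defined by toxicity-caused under-dosing fails the dose test for its own period. Whether it also fails Section 7.4.1 depends on whether 75% applies per period or over 6 weeks, which is not stated.

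**3. Model inputs (Appendix 7, Sections 1 and 3, Table 1).** logit(p) = log α + β log(d/600); log α ~ N(−0.847, SD 1.53); log β ~ N(0, SD 1); correlation 0. Checks: logit(0.3) = −0.847; [logit(0.99) − logit(0.01)]/6 = 9.19/6 = 1.53. At β = 1, the rates at 25 to 600 mg are 1.8, 3.4, 6.7, 12.5, 22.2 and 30.0%, against 2, 4, 7, 13, 22 and 30% in Table 4. Only 50 mg rounds differently, which does not matter here.

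**4. Method.** Binomial likelihood, posterior integrated on a grid. Overdose means a DLT rate of 33% or more. A dose is admissible if P(overdose) < 25% and the increase is at most 100%. Among admissible doses, the one with the highest probability of lying in 16% to 33% is recommended. Assumed: 0/4 at each lower level, and replacements without a DLT.

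**5. Results: same participants, DLTs counted or dropped.**

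| Current dose and data | DLTs counted | DLTs dropped |
|---|---|---|
| 12.5 mg, 2 DLTs in 4 | 2/4: 0.475 at 12.5 mg, none admissible | 0/2: must wait (see below) |
| plus 1 replacement | 2/5: 0.360 at 12.5 mg, none admissible | 0/3: 0.016 at 25 mg, go to 25 mg |
| plus 2 replacements | 2/6: 0.269 at 12.5 mg, none admissible | 0/4: 0.011 at 25 mg, go to 25 mg |
| 100 mg, 2 DLTs in 4 | 2/4: 0.357 at 200 mg, stay | 0/2: 0.024 at 200 mg, go to 200 mg |
| plus 1 or 2 replacements | 0.312 or 0.272, stay | 0.019 or 0.015, go to 200 mg |
| 200 mg, 1 DLT in 4 | 1/4: 0.275 at 400 mg, stay | 0/3: 0.076, go to 400 mg |
| plus 1 replacement | 1/5: 0.245, go to 400 mg | go to 400 mg (no difference) |
| 400 mg, 1 DLT in 4 | 1/4: 0.373 at 600 mg, barred | 0/3: 0.163, go to 600 mg |

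Section 5.1.2.1 allows a decision on two evaluable participants only if a DLT in a third would not alter the recommendation. At 12.5 mg that check (1/3) gives 0.282 at 25 mg, so the trial must wait. At 100 mg it gives 0.157 at 200 mg, so it does not stop escalation. At 400 mg, with DLT-free replacements, 600 mg stays barred at 1/5, 1/6 and 1/7 (0.329, 0.293, 0.262) but not at 1/8 (0.235). The 200 mg row with one replacement depends on the history: 1/5 gives 0.256 (stay) after 0/3 at each lower level and 0.231 after 0/6.

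One DLT in four at 12.5, 25, 50 or 100 mg gives 0.205, 0.095, 0.084 or 0.131 at the next level, so the next dose is the same on either reading.

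**The case against.** The best answer is that the protocol already says DLTs count. The paragraph of Section 5.1.2.1 that holds the 11-of-14 rule also states what the monotherapy model is fitted to, and asks for all available DLT information. The dose minimum can be read as applying to participants without a DLT. The Section 7.4.1 sentence opens with the 6-week period and may describe only those who complete it. The Section 7.2 wording can be read as not covering someone whose DLT has already been determined. Classing toxicity-caused under-dosing as a DLT would have little purpose if those participants were discarded. All of this stands as evidence of intent. It does not remove the contradiction, because Section 7.4.1 uses mandatory wording about escalation decisions and no passage ranks the rules.

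The illustrations are also worst cases: every DLT is dropped and every replacement is DLT-free. At the Table 4 'By Prior' rates, two or more DLTs in four are rare: below 0.25% at 2% (the 25 mg rate) and about 2.7% at 7% (100 mg). That is fair for the low-dose rows. It is less so at 400 mg, where 22% gives 4 × 0.22 × 0.78³ = 0.42 for exactly one DLT in four. These are chances of the DLTs occurring, not of their being dropped.

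The combination model was not fitted, because the appendix does not fix its gamma shape. Since the lower of the two recommendations governs, it could hold the dose down. Investigators and the Medical Monitor also agree each dose in an open-label trial, on all available data. These are real but partial safeguards, since they do not define the model's input.

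**Conclusion.** The wording gap is certain, and it should be fixed. Section 7.4.1 taken literally excludes all lead-in DLT participants from escalation decisions; Section 5.1.2.1 excludes some of them from the monotherapy set. Both conflict with the passages that count DLTs, and Sections 7.2 and 7.4.1 differ on replacement.

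A reader might infer that the trial will discard DLTs, or that the rules as a whole remove them. The documents do not support that, because the counting passages are equally part of the text and most of them point the other way. Nor does every DLT from under-dosing fail both tests, as the 34/42 case shows.

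The size is conditional. The readings diverge with two DLTs in four at 12.5 mg (once a replacement is added) or at 100 mg, and with one in four at 400 mg. They diverge only briefly at 200 mg under the assumed history, and not at all for one in four at 12.5 to 100 mg. This rests on the Table 1 prior, the monotherapy model alone and the assumptions above. It gives no frequency.

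**What to change.** Reconcile Sections 5.1.2.1, 7.2, 7.4.1 and 7.4.1.1 into one analysis definition. For each period's model, a participant is DLT-evaluable if they had a DLT in that period, regardless of doses received, or had no DLT and met the dose and observation minimum. State whether 75% applies per period or over 6 weeks. Make the replacement wording in Section 7.2 consistent with Section 7.4.1, so that participants with a DLT stay in the model.

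Optional: align the 5-day and 21-day minimums, which has little numerical effect because 21 daily doses already span 21 days. Section 10.2 defines no DLT-evaluable set, and Section 10.3.2 reports the DLT rate on treated participants. That keeps every DLT but dilutes the rate with non-evaluable participants who had none, so the rate could be reported on both sets.

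The cost is one clause in Sections 5.1.2.1 and 7.4.1, a matching edit in 7.2 and, if wanted, one analysis set. No participants or procedures are added.
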